4.10. Laboratory Testing

Clinical laboratory parameters will be assessed at screening and at the end of the study. The following tests will be performed at the two time points specified in the protocol: chemistry (A/G ratio, ALT [SGPT], AST [SGOT], albumin, alkaline phosphatase, amylase, bilirubin-direct,

bilirubin-indirect, bilirubin-total, BUN, BUN/creatinine ratio, calcium, carbon dioxide, cholesterol-total, chloride, CPK-total, creatinine, GGT, globulin, glucose, iron-total, LDH, lipase, magnesium, phosphorus-inorganic, potassium, protein-total, sodium, TIBC, triglycerides, uric acid) and hematology (red blood cell count, WBC count, hemoglobin, hematocrit, cell indices, differential, platelet count).

4.11. Blinding of Study Drugs

Subjects and caregivers will be blinded to study treatment. Every subject will receive NAC or matching PLs at every study visit from the baseline visit to the week-45 visit. No study agent will be dispensed at the week-60 visit.

5. Study Endpoints

5.1. Primary Study Endpoint

The primary endpoint will be the change in serial measurements of FVC over the study period.

5.2. Secondary Study Endpoints

5.2.1. Time to Disease-progression

The time-to-death or a 10% decline in FVC will be defined as the time-to-disease progression. The 10% decline in FVC from enrollment must be confirmed on 2 consecutive visits no less than 6 weeks apart. For subjects with 2 consecutive visits with a 10% decline in FVC, the time-to-disease progression will be defined as the time interval between enrollment and the initial visit with a 10% FVC decline. For subjects who experience disease progression, the study doctor will determine whether or not the subject will remain in the study.

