4.4.2.6. Week 60 (Early Withdrawal or Final Treatment Visit)

At week 60, or at subject withdrawal from the study (premature, by study doctor or subject's decision), a final treatment visit will occur. At this final treatment visit subjects will discontinue NAC/PL abruptly. Week 60 activities also include:

- Physical examination
- Measure vital signs with oximetry
- Measure height and weight
- Laboratory values (complete blood count [CBC] and serum chemistries)
- Spirometry (post-bronchodilator) measurement
- 6MWT with Borg scale measurement
- DLCO
- Lung volumes
- ABG
- Review of AEs

- Evaluate for AEx
- Review concomitant medications.
- Subjects will complete all QOL and dyspnea questionnaires (EuroQol, ICE CAP, SF-36, SGRQ, and UCSD SOBQ)
- If consent has been given, blood will be drawn and a urine specimen collected for the biospecimen repository
- Subjects return used and unused study drug for the visit
- Study diary reviewed

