4.5. Dose Justification

The general philosophy for determining dosing levels was to apply previously examined treatment regimens. With the focus of the study being to establish a standard of care for mild/moderate IPF subjects, the goal was to develop flexible yet standardized treatment rules that allow for the temporary or permanent withholding of one or more components of treatment when necessary. Subjects developing laboratory abnormalities or symptoms that result in discontinuation of one or more components of study treatment may continue on the other components as long as there is no contraindication for this. Complete follow-up is important for the validity of any study. As a strategy to maintain protocol adherence, we are using a treatment regimen that will detect potential side effects and prompt interventions proactively in the interest of patient safety. In addition, subjects who permanently stop study medications during the course of the study are encouraged to continue in the study, completing all scheduled visits and tests.

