9.1. General Analytic Considerations

All primary analyses will be based on intent-to-treat (ITT) principles using all randomized subjects. Baseline factors across groups will be compared using mean (standard deviation) and median (25th and 75th percentiles) summary measures. Kaplan-Meier curves will be used to display event rates. Due to clinical interest in departures from both sides of the null hypothesis, all test statistics will be 2-sided.

Reasonable caution needs to be taken when conducting multiple analyses on key clinical subgroups. For subgroup analyses, a conservative significance level of 0.001 will be used for all interaction tests. Thus, subgroup comparisons will be considered exploratory unless the p-value from the interaction test is smaller than 0.001.

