9.7. Power Analysis

9.7.1. Primary Analyses

Based on previously published IPF clinical trials, the PL group is expected to experience a drop in FVC of approximately 0.20 L over the study period (see Figure 1). The IPFnet Steering Group determined a clinically important difference would be to preserve the majority of the decline relative to PL over the study period. In particular, a treatment effect of 0.15 L was determined to be a clinically meaningful difference. Potential dropout is a key factor in the proposed study. The drop-out process assumed 5% lost to follow-up after every study visit. Only 80% of subjects were assumed to be followed for the entire study period. All models assumed a compound symmetry structure for the covariance matrix. Power calculations were performed using a SAS IML program for designing repeated measures studies.⁴⁶ Based on preliminary reviews of the data from the University of Michigan, the covariance matrix parameters were estimated at approximately $\sigma^2 = 0.757$ (variance parameter) and $\rho = 0.936$ (correlation parameter). To be conservative, the power calculations for the primary analysis were performed with parameter setting of $\sigma^2 = 0.810$ (variance parameter) and $\rho = 0.925$ (correlation parameter).

The power calculations assume a correction for imperfect compliance proposed by Lachin and Foulkes to allow for 2% noncompliance for each of the treatment arms.⁴⁷ Thus, the sample size of 130 subjects per arm would be reduced to an adjusted sample size of $130 \times (1 - 0.02 - 0.02)^2 = 119.8$ or 120 subjects per arm.

Under the assumed Type I error rate of 0.05, with a correlation parameter of 0.925 and standard deviation of 0.90, the difference of 0.15 L (or 0.0025 L/week) shown in Table 6 would have power of 93%.

Table 6: Hypothetical Values of Mean FVC (L) Change from Baseline

	Week 15	Week 30	Week 45	Week 60
NAC	0.0125	0.0250	0.0375	0.0500
Placebo	0.0500	0.1000	0.1500	0.2000
Difference	0.0375	0.0750	0.1125	0.1500

Abbreviations: FVC, forced vital capacity; PL, placebo

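### Section 5.2.1 lets the study doctor, without criteria, end follow-up after a confirmed 10% FVC decline, so later FVC and event data may go uncollected; reconcile it with Sections 4.5 and 4.4.2.6

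*Protocol*

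**What the plan says.** - Section 5.1: "The primary endpoint will be the change in serial measurements of FVC over the study period".
- Section 5.2.1 defines disease progression as death or a 10% FVC decline, and adds: "The 10% decline in FVC from enrollment must be confirmed on 2 consecutive visits no less than 6 weeks apart". It then says: "For subjects who experience disease progression, the study doctor will determine whether or not the subject will remain in the study". No criteria are given. The sentence speaks of the study, not of study drug.
- Section 4.4.2.6 holds the final treatment visit at week 60 or "at subject withdrawal from the study (premature, by study doctor or" by the subject's own choice. Spirometry and the other end-of-study tests are done then, and no later scheduled visit follows except a possible FVC confirmation visit (4.4.2.7) and the four-week safety call (4.4.2.8).
- Section 4.5 ties the validity of a study to complete follow-up and says "subjects who permanently stop study medications during the course of the study are encouraged to continue in the study, completing all scheduled visits and tests".
- Section 3.7 lists keeping dropout similar between arms among the reasons for blinding.
- Section 5.2.2 keeps subjects with a suspected acute exacerbation in the study.
- Section 9.1: "All primary analyses will be based on intent-to-treat (ITT) principles using all randomized subjects". Section 9.4 imputes no missing FVC, and Section 9.5 relies on missing at random (MAR).
- Section 9.7.1 assumes a flat 5% loss after every visit: "Only 80% of subjects were assumed to be followed for the entire study period".

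**The concern.** The event that opens the way to removal is a value of the primary variable. If one arm declines faster, which is the trial's hypothesis, that arm produces more candidates for removal. Differential dropout could then come from the protocol itself.

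Three things are at stake:

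- **Precision.** The late visits, which carry most information on a slope, are the ones lost.
- **MAR.** The primary model holds treatment, time, their interaction, age, sex, race and height. A discretionary decision can also draw on symptoms, oxygenation or frailty, which the model does not contain.
- **Events.** Section 3.6 calls a 10% FVC fall a strong predictor of survival, and mortality and time to death head the secondary aims in Section 2.3. Adverse-event recording stops four weeks after the last dose (6.1.2), and the protocol describes no collection of vital status after withdrawal. The subjects whose follow-up may be cut short are therefore those the protocol marks as at high risk of death.

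**Working it through.** **1. Which values are at risk.** FVC is measured at weeks 0, 15, 30, 45 and 60, and a decline must hold at two consecutive visits. On scheduled visits:

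- confirmed at week 30 (declines at 15 and 30): weeks 45 and 60 can be lost;
- confirmed at week 45: week 60 can be lost;
- confirmed at week 60: nothing is lost.

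Values up to and including the withdrawal visit are kept.

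**2. Inputs from Section 9.7.1.** Decline over 60 weeks is 0.20 L on placebo and 0.05 L on NAC, a difference of 0.15 L. Covariance is compound symmetry with σ² = 0.81 and ρ = 0.925. Loss is 5% after each visit, so 0.95⁴ = 0.81 complete. Adjusted size is 130 × (1 − 0.02 − 0.02)² = 119.8, or 120 per arm. Alpha is 0.05, two-sided.

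**3. Reproducing the stated power.** The standard error (SE) of the treatment-by-time slope comes from the generalised least squares information, the sum over subjects of X′V⁻¹X, using the visits each subject has. Power = Φ(0.15/SE − 1.96).

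- 5% loss per visit: SE = 0.0437; 0.15/0.0437 = 3.43; Φ(1.47) = 93.0%.
- Linear loss to 80% complete: SE = 0.0439; power 92.7%.

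The protocol's 93% is reproduced.

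**4. Adding removal of confirmed progressors (simulation).** Assumptions not in the protocol: a 10% fall equals 0.20–0.35 L (baseline FVC 2.0–3.5 L), removal applies to half or all confirmed progressors, and it comes on top of the 5% loss. Subjects removed are counted only if they would otherwise have reached the next visit.

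| Covariance (σ², ρ) | Removal | Removed, placebo / NAC | Week-60 completion, placebo / NAC | SE | Power |
|---|---|---|---|---|---|
| 0.81, 0.925 | none | 0 / 0 | 81% / 81% | 0.0437 | 93% |
| 0.81, 0.925 | half | 7–13% / 4–9% | 69–75% / 73–77% | 0.0447–0.0458 | 91–92% |
| 0.81, 0.925 | all | 13–25% / 9–19% | 57–69% / 64–73% | 0.0458–0.0483 | 87–91% |
| 0.757, 0.936 | none | 0 / 0 | 81% / 81% | 0.0390 | 97% |
| 0.757, 0.936 | half | 6–12% / 3–9% | 70–76% / 73–78% | 0.0398–0.0408 | 96–97% |
| 0.757, 0.936 | all | 11–24% / 7–17% | 58–70% / 65–75% | 0.0405–0.0428 | 94–96% |

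Lowest case: 0.15/0.0483 = 3.11; Φ(1.15) = 87.4%. Simulation noise moves this end between 87% and 88%.

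**5. Bias.** When removal depends only on recorded FVC, the likelihood estimate stays at 0.150 L and type I error stays near 5%. In one illustrative case where the doctor also acts on worsening not in the recorded FVC, the estimate is 0.143–0.144 L under compound symmetry and 0.148–0.149 L under an assumed random-slope covariance. That is one mechanism, not a bound.

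**6. Events.** The protocol gives no event rates, so no figure can be put on the loss of deaths, exacerbations or hospitalisations.

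**The case against.** A reader might infer that the rule deletes primary data as soon as FVC falls 10%, and that it contradicts intent-to-treat. The documents support neither. The decline must be confirmed, removal is allowed and not required, and no collected value is discarded. Section 9.1 defines who is analysed, and a removed subject remains in the likelihood model with the visits made. Section 4.5 speaks of subjects who stop drug, and only encourages them to stay. Both sections can be followed, so this is a tension and not a flat contradiction.

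The defence has more to say:

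- The planning covariance is deliberately conservative. With the protocol's estimates, even removal of every progressor leaves at least 94% power, above the stated 93%.
- Section 9.7.1 does not say which reasons for loss its 5% covers, so adding progression removals may count some twice.
- Subjects and caregivers are blinded, so discretion cannot knowingly favour an arm.
- Sections 9.2 and 9.5 plan to examine dropout by arm and reasons for discontinuation, to run MAR sensitivity analyses, and to report vital status in the flow diagram.

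These points stand, and they limit the severity. They do not remove the concern. Blinding does not stop the faster-declining arm from producing more removals, and no sensitivity analysis restores FVC or deaths that were never collected.

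**Conclusion.** The concern holds as a moderate design weakness. Section 5.2.1 permits follow-up to end, at one doctor's discretion and without criteria, because of the primary variable. It is in tension with the retention policy in Section 4.5, with the aim in Section 3.7 of keeping dropout similar across arms, and with the flat loss rate in Section 9.7.1.

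For the primary analysis the harm is limited: about 2–6 points of power under the planning covariance if all confirmed progressors go, 1–2 points if half go, and no likelihood bias while decisions follow recorded FVC alone. The size rests on the assumed 0.20–0.35 L threshold and removal fractions. Bias from decisions that use other information is possible and unquantified. Censoring of deaths and other events may be informative, and those data could not be recovered.

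**What to change.** Reconcile Sections 5.2.1, 4.4.2.6 and 4.5 so that staying in follow-up is separate from any decision on study drug. In place of the last sentence of Section 5.2.1, a wording such as: *Disease progression alone is not a reason to end follow-up. Scheduled FVC visits and collection of vital status continue to week 60 unless the subject withdraws consent or cannot attend.* Add a cross-reference in Section 4.4.2.6.

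Leave study-drug decisions, and withdrawal by the study doctor for other reasons, to the existing sections. Striking study-doctor withdrawal from Section 4.4.2.6 altogether would go further than this point supports.

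The cost is amendment wording and a notice to sites. The visits are already in Table 3 and telephone contact in Section 4.4.2.9, so no new procedure is needed. The protocol shows no budget, so the cost of the retained visits cannot be stated.

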5.2.2. Acute Exacerbations

The following 3 criteria will define AEx in subjects with acute worsening of their respiratory conditions:

1. Clinical (all of the following required):
 - A) Unexplained worsening of dyspnea or cough within 30 days, triggering unscheduled medical care (e.g., emergency room, clinic, study visit, hospitalization).
 - B) No clinical suspicion or overt evidence of cardiac event, pulmonary embolism, or deep venous thrombosis to explain acute worsening of dyspnea.
 - C) No pneumothorax.

2. Radiologic/Physiologic (A and B required):
 - A) New ground glass opacity or consolidation computed tomography (CT) scan, OR new alveolar opacities on chest x-ray.
 - B) Decline of $\geq 5\%$ in resting room air SpO₂ from last recorded level OR decline of ≥ 8 mm Hg in resting room air PaO₂ from last recorded level.

3. Microbiologic (all of the following required):
 - A) No clinical evidence for infection (i.e., absence of grossly purulent sputum, fever $> 39^{\circ}\text{C}$ orally).
 - B) Lack of positive microbiological results (if done) from lower respiratory tract defined as:
 - (1) Clinically significant bacterial growth on sputum or endotracheal aspirate cultures;
 - (2) Quantitative culture by protected brush specimen $\geq 10^3$ cfu/mL or BAL $\geq 10^4$ cfu/mL;
 - (3) The presence of specific pathogens on stains of any of the above.
 - C) Lack of positive pathogen in blood cultures (if done).

Identification of Acute Exacerbations

All subjects will be educated about the importance of identifying AExs. At the time of enrollment, subjects will be told about the possibility of developing acute symptomatic worsening that might represent an AEx of IPF, and instructed to contact their study clinical center coordinator within 48 to 72 hours of the apparent event.

All subjects will be contacted by phone monthly, and questioned about any change in dyspnea or cough and any interim clinic visits or hospitalizations. Finally, as part of the IPFnet outreach to community referring physicians, the importance of AExs will be emphasized. When a subject is identified who meets criterion 1A, this will trigger the collection of additional clinical data to evaluate a suspected AEx. These data will be collected as part of standard clinical care (i.e., this protocol does not require collection of all items). The additional items to be collected for suspected AEx include:

- IPFnet AEx case report form (eCRF) (required)

- Chest x-ray, CT scan with/without pulmonary angiogram (reports should be faxed and followed by the hard copies/discs)
- Oxygen saturation (pulse oximetry)
- ABG
- Respiratory cultures (sputum, endotracheal aspirate, lavage)
- Blood cultures
- Clinic/hospital records related to the event

All potential cases of AEx will be reviewed by the clinical center PI first, and a decision on whether the case may represent an AEx will be made. If AEx is suspected, the case will be sent to the IPFnet adjudication committee, which will assign a final diagnosis (see Table 5). If there is disagreement among members, the majority opinion will be recorded.

During episodes of suspected AEx, as determined by the individual clinical center investigator, subjects will remain blinded and in the study.

Table 5: Final Diagnoses in Evaluation of Suspected Acute Exacerbations

Definite acute exacerbation	All criteria met; no alternative etiology
Unclassifiable acute worsening	Insufficient data to evaluate all criteria; no alternative etiology
Not acute exacerbation	Alternative etiology identified that explains acute worsening

Management of the suspected AEx will be at the discretion of the treating physician. Standard of care generally involves evaluation for respiratory infection, pulmonary embolism, cardiac events and pneumothorax, and treatment with IV corticosteroids.

Study drugs will be resumed at pre-suspected AEx doses after subjects clinically improve as confirmed by the local PI. All subjects should be seen at the clinical center within 2 to 4 weeks of recovery for measurement of post-bronchodilator FVC (see Figure 4). Subjects unable to return to the clinical center after suspected AEx due to medical frailty (e.g., continued

institutionalization, progressive disability) will be categorized as failing to maintain FVC response in secondary analyses.

[figure not shown]

Figure 4. Acute Exacerbation Flow Chart

5.2.3. Respiratory Infections

An upper respiratory infection will be defined as:

- Change in sputum discoloration
- Increased cough of no more than 14 days' duration

A lower-respiratory infection (pneumonia) will be defined as new segmental or lobar airspace opacities visualized by image studies (chest radiograph or HRCT) in addition to any of the following:

- Positive pathogen/cultures in good sample of sputum or lower-airway secretions retrieved by fiberoptic bronchoscope
- Fever > 39°C or > 100°F
- Leukocytosis > 12,000 (unexplained; no increase in dose of corticosteroids)

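### The pneumonia fever limit names two different temperatures, its overlap with the exacerbation infection test is left unresolved, and Table 5 leaves one kind of case without a category

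*Protocol*

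**What the plan says.** **Pneumonia (section 5.2.3).** "A lower-respiratory infection (pneumonia) will be defined as new segmental or lobar airspace opacities visualized by image studies", together with any one of three further findings: a positive pathogen or culture, fever, or a raised white count. The fever item reads "Fever > 39°C or > 100°F". The white-count item reads "Leukocytosis > 12,000 (unexplained; no increase in dose of corticosteroids").

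**Acute exacerbation (section 5.2.2).** Three groups of criteria must be met.

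- Criterion 1A requires that the worsening be unexplained.
- Criterion 2A asks for "New ground glass opacity or consolidation computed tomography (CT) scan, OR new alveolar opacities on chest x-ray", and 2B for a fall in SpO2 of at least 5% or in PaO2 of at least 8 mm Hg.
- Criterion 3A begins "No clinical evidence for infection (i.e., absence of grossly purulent sputum, fever" and sets the fever at above 39°C orally. It gives no Fahrenheit value and no white-cell item.
- Criterion 3B is worded "Lack of positive microbiological results (if done) from lower respiratory tract defined as", so cultures count only where they were taken.

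**Adjudication (section 5.2.2, Table 5).** The committee assigns one of three final diagnoses. *Definite* needs every criterion met and no other cause. *Unclassifiable* needs too little data to judge all criteria and no other cause. *Not acute exacerbation* is defined only as "Alternative etiology identified that explains acute worsening".

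**Endpoints (section 2.3).** Exacerbation frequency is item 3 of the secondary goals; infectious and noninfectious respiratory complications are item 16.

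**The concern.** The fever line in 5.2.3 looks like one limit written in two units, but the values do not convert into each other. The lower value also disagrees with the limit that 5.2.2 uses to rule infection out. The two definitions accept similar imaging, since lobar consolidation on CT can satisfy both. The clinical signs of infection are then what separates the two event types when cultures are negative or were not taken, and those signs are set differently in the two sections.

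At stake is whether the counts of exacerbations and of infectious complications can be reproduced from the written rules. If the same event can satisfy both, the reported split between them rests on judgement that the protocol does not describe. The Table 5 gap is a separate defect: the committee must give a final diagnosis to every case it receives, and for one kind of case no row applies.

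**Working it through.** **1. Unit conversion.** Inputs: 39°C and 100°F, both from 5.2.3.

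- 39 × 9/5 + 32 = 102.2°F.
- (100 − 32) × 5/9 = 37.78°C.
- Gap: 39 − 37.78 = 1.22°C, or 102.2 − 100 = 2.2°F.

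The two values are joined by *or*. Any temperature above 39°C is also above 37.78°C, so the rule reduces to above 37.8°C and the 39°C limb never changes a classification.

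**2. Pneumonia rule against criteria 2 and 3 of the exacerbation rule.** Assume new lobar consolidation, SpO2 down by at least 5%, sputum not purulent, and cultures negative or not taken.

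| Temperature | White count > 12,000 | Meets 5.2.3 pneumonia | Passes exacerbation criteria 2 and 3 |
|---|---|---|---|
| 37.0°C | no | no | yes |
| 37.0°C | yes | yes | yes |
| 38.4°C | no | yes (38.4 > 37.8) | yes (38.4 is not > 39) |
| 38.4°C | yes | yes | yes |
| 39.5°C | either | yes | no |

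Three combinations satisfy both: two with fever between the limits, and one with leukocytosis and no fever.

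**3. Does aligning the temperature remove the overlap?**

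- With 39°C alone in both sections, the 38.4°C case without leukocytosis no longer overlaps. The cases with leukocytosis at 37.0 and 38.4°C still do.
- With 37.8°C in both sections, neither 38.4°C case overlaps. The 37.0°C case with leukocytosis still does.

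Either alignment removes the overlap due to fever alone; neither removes the one due to leukocytosis.

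**4. Table 5.** Enumerate whether all criteria are met, whether the data suffice to judge them all, and whether another cause is found. A case with all criteria met but insufficient data is impossible, which leaves six combinations.

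| All met | Data sufficient | Other cause | Row |
|---|---|---|---|
| yes | yes | yes | Not |
| yes | yes | no | Definite |
| no | yes | yes | Not |
| no | yes | no | **none** |
| no | no | yes | Not |
| no | no | no | Unclassifiable |

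Five combinations map to exactly one row and one maps to none. An example of the last: SpO2 down 3%, PaO2 down 5 mm Hg, everything else met, nothing else found.

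**5. Which defect causes what.** The overlap in step 2 comes from the mismatch between 5.2.3 and criterion 3A. The gap in step 4 leaves a case unlabelled. Table 5 as written never puts one case in two rows, so it cannot produce a double count.

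**The case against.** The strongest reply is that passing criterion 3A is necessary for an exacerbation but not sufficient. Criterion 1A wants unexplained worsening, and the *Definite* row of Table 5 also requires that there be no other cause. An event that meets a definition labelled pneumonia is an obvious candidate for another cause, and the committee can then record it as not an exacerbation. This stands, and it is why double counting is only possible. It does not dispose of the point, because no text shown says that meeting 5.2.3 counts as another cause or that the two event types exclude each other. Figure 4, the exacerbation flow chart, is not available here and might add such a rule; it could not make 39°C equal to 100°F.

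Three further replies also stand.

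- A reader might infer that everyone between 37.8 and 39°C is classified in conflict. The documents do not support that: the imaging, the oxygenation fall, non-purulent sputum, cultures negative or not taken, referral by the site investigator and a finding of no other cause must all coincide.
- A reader might infer that exacerbation counts vary with the thermometer unit. Criterion 3A has one temperature, so its result does not depend on the unit. In 5.2.3 the literal *or* gives a determinate limit; the risk is that a site reads only the Celsius figure.
- A reader might infer that the Table 5 gap inflates or distorts the exacerbation count. The three criteria define an exacerbation, so a fully evaluated case that fails one cannot be *Definite*. What is missing is a label for a non-case.

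It can also be said that a rule for diagnosing pneumonia and a rule for excluding infection need not share a cut-off. That is fair in principle, but an intended difference should be stated along with how cases between the limits are handled.

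**Conclusion.** The concern holds in limited form. The fever limit in 5.2.3 is faulty as written: two values 1.2°C (2.2°F) apart, one of them without effect. It is also inconsistent with criterion 3A. An event can satisfy the pneumonia definition and the exacerbation no-infection test through fever between 37.8 and 39°C or through leukocytosis alone, and the written rules do not say how it should be counted. Independently, Table 5 leaves one of six feasible combinations without a category.

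The effect is confined to two secondary counts, items 3 and 16 of section 2.3. The primary FVC analysis and the sample size are untouched. The protocol gives no event rates, so the number of affected cases cannot be estimated. The conclusion assumes that Figure 4 contains no rule that settles the overlap or the gap. The stronger reading, that events will be counted twice and that Table 5 is the reason, is not supported: adjudicators have room to call the event pneumonia, and Table 5 plays no part in the overlap. Which temperature is right is a clinical question that the documents do not answer.

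**What to change.** 1. In 5.2.3, reconcile the two temperatures into one limit stated consistently in °C and °F, and reconcile it with criterion 3A of 5.2.2. The committee must choose the value.
2. State whether an event that meets the 5.2.3 pneumonia definition, including through leukocytosis alone, counts as an alternative etiology in exacerbation adjudication. Step 1 alone does not close the leukocytosis route.
3. In Table 5, extend *Not acute exacerbation* to cases where at least one evaluated criterion is not met or another cause is identified. Limit *Unclassifiable* to cases with insufficient data, no evaluated criterion failed and no other cause. Both changes are needed: widening the last row alone would put a case with one criterion failed and another not evaluable in two rows. With both, another cause or any failed criterion leads to *Not*; otherwise complete data lead to *Definite* and incomplete data to *Unclassifiable*, so the rows are exhaustive and exclusive.

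The cost is a few lines of protocol and adjudication wording, plus a blinded re-check of any adjudicated cases affected: those with temperatures between the two limits, those with leukocytosis as the only sign of infection, and those with a failed criterion and no other cause. Some cases with one criterion failed and another not evaluable would move from *Unclassifiable* to *Not*.
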